#### 6.1.1 Dosing regimen

All patients will take everolimus/placebo as a daily dose of 10 mg (2 × 5 mg tablets at same time) orally continuously per day and exemestane 25 mg (one tablet) orally per day. Everolimus tablets should be swallowed whole with a glass of water once daily. Tablets should not be chewed or crushed. Exemestane will be self-administered as described in [Table 6-1](#) and taken together with everolimus. Both drugs will be taken after a meal at the same time each day in the morning.

**Table 6-1 Dose and treatment schedule**

Study treatments	Pharmaceutical form and route of administration	Dose	Frequency and/or Regimen
everolimus/placebo	Tablets for oral use	10 mg (2 × 5 mg)	Daily
exemestane	Tablets for oral use	25mg	Daily

#### 6.1.2 Ancillary treatments

Not applicable.

#### 6.1.3 Rescue medication

Not applicable.

#### 6.1.4 Guidelines for continuation of treatment

For guidelines for continuation of treatment, refer to [Section 6.3 Dosing modifications](#).

Patients who permanently discontinue one of the study treatments for any reason other than disease progression may continue the other study treatment as part of the trial therapy at the investigators discretion until disease progression, unacceptable toxicity, death or discontinuation from study treatment due to any other reason and should follow the protocol safety and efficacy assessments as scheduled. After discontinuing study treatment, further treatment is left to the physician's discretion.

### **6.1.5 Treatment duration**

Patients may be discontinued from treatment earlier due to:

- Disease progression according to RECIST 1.1 as determined by investigator.
- Unacceptable toxicity
- Discontinued treatment at the discretion of the investigator or the patient
- Death
- Patient is lost to follow-up
- Withdraw the consent
- Protocol deviation
- Study termination by sponsor
- Technical problems

## **6.2 Dose escalation guidelines**

Not applicable.

## **6.3 Dose modifications**

### **6.3.1 Dose modification and dose delay**

#### **Everolimus**

For patients who do not tolerate the protocol-specified dosing schedule, dose adjustments are permitted in order to allow the patient to continue the study treatment. The following guidelines may be applied:

If dose reduction is required, the suggested dose is approximately 50% lower than the daily dose previously administered ([Table 6-2](#)). If a patient has already decreased 2 dose levels, no further dose reduction is permitted.

Patients requiring an additional dose reduction will be required to discontinue study treatment. Patients who interrupt therapy for more than 4 weeks must be discontinued from the study.

These changes must be recorded on the Dosage Administration Record CRF.

**Table 6-3 Criteria for interruption and re-initiation of everolimus/placebo treatment**

Recommended dose modifications for everolimus/placebo	
Worst toxicity CTCAE Grade (value)	During a cycle of therapy
Hematologic	
Neutropenia (ANC)	
Grade 1 (ANC < LLN - 1500/mm  )	Maintain dose level
Grade 2 (ANC < 1500 - 1000/mm  )	Maintain dose level
Grade 3 (ANC < 1000 - 500/mm  )	Omit dose until resolved to ≤ Grade 2, then maintain dose level
Grade 4 (ANC < 500/mm  )	Omit dose until resolved to ≤ Grade 2, then ↓ 1 dose level
Thrombocytopenia	
Grade 1 (PLT < LLN - 75,000/mm  )	Maintain dose level
Grade 2 (PLT < 75,000 - 50,000/mm  )	Temporary dose interruption until recovery to Grade ≤1. Re-initiate everolimus at the same dose.
Grade 3 (PLT < 50,000 - 25,000/mm  )	Temporary dose interruption until recovery to Grade ≤1. Re-initiate treatment at a lower dose.
Grade 4 (PLT < 25,000/mm  )	Temporary dose interruption until recovery to Grade ≤1. Re-initiate treatment at a lower dose.
Febrile neutropenia	
Grade 3 (ANC<1.0x10  /L with single temperature >38.3°C (101°F) or sustained temperature ≥38°C (100.4°F) for >1h)	Temporary dose interruption until recovery of (ANC≥1.25x10  /L) and no fever. Re-initiate everolimus at a lower dose.
Grade 4 (Life-threatening consequences; urgent intervention indicated)	Discontinue everolimus.
Any hematologic toxicity requiring study drug interruption for >28 days	Discontinue everolimus.
Hepatic	
Isolated AST or ALT elevation	
> ULN - 3.0 × ULN	Maintain dose level

Recommended dose modifications for everolimus/placebo	
Worst toxicity CTCAE Grade (value)	During a cycle of therapy
> 3.0 - 5.0 × ULN For patients with baseline value ≤ 3.0 × ULN	Maintain dose level. Repeat LFTs b as soon as possible, preferably within 48-72 hours from awareness of the abnormal results; if abnormal lab values are confirmed upon the repeat test, then monitor LFTs b weekly, or more frequently if clinically indicated, until resolved to ≤ 3.0 × ULN
For patients with baseline value > 3.0 -5.0 × ULN	Maintain dose level
> 5.0 - 10.0 × ULN For patients with baseline value ≤ 3.0 × ULN	Omit dose. Repeat LFTs b as soon as possible, preferably within 48-72 hours from awareness of the abnormal results; monitor LFTs b weekly, or more frequently if clinically indicated, until resolved to ≤ 3.0 × ULN. Then If resolved in ≤ 14 days, maintain dose level If resolved in > 14 days, ↓ 1 dose level
For patients with baseline value > 3.0 -5.0 × ULN	Maintain dose level. Repeat LFTs b as soon as possible, preferably within 48-72 hours from awareness of the abnormal results; if abnormal lab values are confirmed upon the repeat test, then monitor LFTs b , weekly, or more frequently if clinically indicated, until resolved to ≤ 5.0 × ULN
> 10.0 - 20.0 × ULN	Omit dose. Repeat LFTs b as soon as possible, preferably within 48-72 hours from awareness of the abnormal results; monitor LFTs b weekly, or more frequently if clinically indicated, until resolved to ≤ baseline. Then ↓ 1 dose level.
> 20.0 × ULN	Omit dose. Repeat LFTs b as soon as possible, preferably within 48-72 hours from awareness of the abnormal results; monitor LFTs b weekly, or more frequently if clinically indicated, until resolved to ≤ 3 × ULN (or ≤ 5 × ULN for patients with baseline value > 3.0 -5.0 × ULN), then resume treatment at ↓ 1 dose level. Only 1 dose reduction is allowed; if reoccurs at > 5 × ULN, discontinue patient from study treatment.
Combined c elevations of AST or ALT and total bilirubin	
For patients with normal baseline ALT and AST and total bilirubin value: AST or ALT >3.0xULN combined with total bilirubin >2.0 x ULN without evidence of cholestasis d OR (Note to study team: If supported by available data) For patients with elevated baseline AST or ALT or total bilirubin value [AST or ALT>2x baseline AND > 3.0 xULN] OR [AST or ALT > 8.0 xULN], combined with [total bilirubin >2x baseline AND >2.0 ×ULN]	Permanently discontinue patient from study treatment.  Repeat as soon as possible, preferably within 48 hours from awareness of the abnormal results, then with weekly monitoring of LFTs b ), or more frequently if clinically indicated, until AST, ALT, or bilirubin have resolved to baseline or stabilization over 4 weeks. Refer to Section 6.3.2.1 for additional follow-up evaluations as applicable.
Metabolic (e.g. hyperglycemia, dyslipidemia)	
Grade 1	Maintain dose level, initiate appropriate medical therapy and monitor
Grade 2	Maintain dose level, manage with appropriate medical therapy and monitor
Grade 3	Omit dose until resolved to ≤ grade 1, then ↓ 1 dose level
Grade 4	Discontinue patient from study treatment, and treat with appropriate medical

Recommended dose modifications for everolimus/placebo	
Worst toxicity CTCAE Grade (value)	During a cycle of therapy
Non-infectious pneumonitis	See Section 6.3.2.1 .
Stomatitis	See Section 6.3.2.2 .
Other non-hematologic toxicities (excluding metabolic events)	
Grade 1	If toxicity is tolerable, no dose adjustment required. Initiate appropriate medical therapy and monitor.
Grade 2	If toxicity is tolerable, no dose adjustment required. Initiate appropriate medical therapy and monitor. If toxicity becomes intolerable, temporary dose interruption until recovery to Grade $\leq 1$ . Re-initiate everolimus at the same dose. If toxicity recurs at Grade 2, interrupt everolimus until recovery to Grade $\leq 1$ . Re-initiate everolimus at a lower dose.
Grade 3	Temporary dose interruption until recovery to Grade $\leq 1$ . Initiate appropriate medical therapy and monitor. Consider re-initiating everolimus at a lower dose. If toxicity recurs at Grade 3, consider discontinuation.
Grade 4	Discontinue everolimus and treat with appropriate medical therapy.
All dose modifications should be based on the worst preceding toxicity.	
a Common Toxicity Criteria for Adverse Events (CTCAE Version 4.03)	
b Core LFTs consist of ALT, AST, GGT, total bilirubin (fractionated [direct and indirect], if total bilirubin $> 2.0 \times$ ULN), and alkaline phosphatase (fractionated [quantification of isoforms], if alkaline phosphatase $> 2.0 \times$ ULN.)	
c "Combined" defined as total bilirubin increase to the defined threshold concurrently with ALT/AST increase to the defined threshold	
If combined elevations of AST or ALT and total bilirubin do not meet the defined thresholds, please follow the instructions for isolated elevation of total bilirubin and isolated elevation of AST/ALT, and take a conservative action based on the degree of the elevations (e.g. discontinue treatment at the situation when omit dose is needed for one parameter and discontinue treatment is required for another parameter). After all elevations resolve to the defined thresholds that allow treatment re-initiation, re-start the treatment either at the same dose or at one dose lower if meeting a criterion for dose reduction	

## 6.3.2 Additional management and follow-up for selected toxicities

### 6.3.2.1 Management of infections

Everolimus has immunosuppressive properties and may predispose patients to bacterial, fungal, viral or protozoal infections, including infections with opportunistic pathogens. Localized and systemic infections, including pneumonia, other bacterial infections, invasive fungal infections, such as aspergillosis, candidiasis or pneumocystis jirovecii pneumonia (PJP) and viral infections including reactivation of hepatitis B virus, have been described in patients taking everolimus. Some of these infections have been severe (e.g. leading to sepsis, respiratory or hepatic failure) and occasionally have had a fatal outcome.

Physicians and patients should be aware of the increased risk of infection with everolimus. Treat pre-existing infections prior to starting treatment with everolimus. While taking everolimus, be vigilant for symptoms and signs of infection; if a diagnosis of infection is made, institute appropriate treatment promptly and consider interruption or discontinuation of everolimus.

Patients with positive results of HBV-DNA and/or HBsAg at screening should begin a prophylaxis treatment for 1-2 week prior to beginning everolimus therapy. Patients should have HBV-DNA monitored frequently throughout the course of everolimus therapy for signs of hepatitis reactivation.

If a diagnosis of invasive systemic fungal infection is made, discontinue everolimus and treat with appropriate antifungal therapy.

Cases of PJP, some with fatal outcome, have been reported in patients who received everolimus. PJP may be associated with concomitant use of corticosteroids or other immunosuppressive agents. Prophylaxis for PJP should be considered when concomitant use of corticosteroids or other immunosuppressive agents is required.

### **6.3.2.2 Management of non-infectious pneumonitis**

Non-infectious pneumonitis is a known side effect of rapamycin analogues. Clinically significant pneumonitis is typically accompanied by non-specific symptoms including dyspnea, nonproductive cough, fatigue, and fever. Diagnosis is generally suspected in individuals receiving mTOR inhibitors who develop these symptoms or in asymptomatic individuals in whom a routine chest CT scan reveals a new ground glass or alveolar infiltrate.

The frequency of symptomatic pulmonary toxicity (all grades) was approximately 13% in a phase III study of everolimus in patients with metastatic renal cell carcinoma [CRAD001C2240]. Severe (CTC grade 3) pneumonitis occurred in 4% of patients, and an occasional fatality was reported. The lung toxicity was partly or completely reversible in the majority of cases with interventions including drug interruption, discontinuation and the use of corticosteroids.

Individuals participating in this trial will be routinely questioned as to the presence of new or changed pulmonary symptoms consistent with lung toxicity. CT scans and pulmonary function test should be done, as clinically indicated, if there are symptoms that indicate that the patient has developed non-infectious pneumonitis. If non-infectious pneumonitis develops, the guidelines in [Table 6-4](#) should be followed. Dose modification instructions are also provided in [Table 6-4](#). Consultation with a pulmonologist is recommended for any case of pneumonitis that develops during the study.

**Table 6-4 Management of non-infectious pneumonitis**

Worst Grade Pneumonitis	Required Investigations	Management of Pneumonitis	EVEROLIMUS/placebo Dose Adjustment
Grade 1	CT scans with lung windows. Repeat at least every 8 weeks until return to within normal limits.	No specific therapy is required	Administer 100% of study treatment dose.
Grade 2	CT scan with lung windows. Consider pulmonary function testing includes: spirometry, DLCO, and room air O  saturation at rest. Repeat at least every 8 weeks until return to within normal limits. Consider a bronchoscopy with biopsy and / or BAL.	Symptomatic only. Consider corticosteroids if symptoms are troublesome.	Reduce study treatment dose by 1 dose level (see Table 6-2 ) until recovery to < Grade 1. Study treatment may also be interrupted if symptoms are troublesome. Patients will discontinue study treatment if they fail to recover to < Grade 1 within 28 days.
Grade 3	CT scan with lung windows pulmonary function testing includes: spirometry, DLCO, and room air O  saturation at rest. Repeat at least every 6 weeks until return to within normal limits. Bronchoscopy with biopsy and / or BAL is recommended.	Consider corticosteroids if infective origin is ruled out. Taper as medically indicated.	Hold treatment until recovery to < Grade 1. May restart study treatment within 28 days at a reduced dose (by one level) if evidence of clinical benefit.
Grade 4	CT scan with lung windows and required pulmonary function testing, if possible, includes: spirometry, DLCO, and room air O  saturation at rest. Repeat at least every 6 weeks until return to within normal limits. Bronchoscopy with biopsy and / or BAL is recommended if possible.	Consider corticosteroids if infective origin is ruled out. Taper as medically indicated.	Discontinue treatment.

### 6.3.2.3 Guidelines for the prevention and the treatment of study drug induced stomatitis/oral mucositis/mouth ulcers

For prevention the stomatitis, all patients will be instructed to perform routine “good oral care” each day during the trial. Good oral care will consist of: brushing teeth at least twice daily with soft bristled toothbrush, continue current daily flossing routine (if patients were not already flossing daily, they should not be instructed to start flossing as this could cause oral trauma), and continue routine dental care/maintenance with their dentist, if they have one. It is recommended that patients should use 10mL of an alcohol-free, 0.5mg/5mL dexamethasone steroid mouthwash swishing and spitting QID, especially during the first 8 weeks of treatment (majority of stomatitis events occur within the first 8 weeks of treatment). The mouthwash is to be held in mouth and swished around mouth to come in contact with entire buccal mucosa surface for a minimum of two minutes, and then spat out.

Patients with a clinical history of stomatitis/mucositis/mouth ulcers and those with gastrointestinal morbidity associated with mouth/dental infections, irritation of esophageal

mucosa e.g. gastroesophageal reflux disease (GERD) and pre-existing stomatitis/mucositis must be monitored even more closely. Patients should be instructed to report the first onset of buccal mucosa irritation/reddening to their study physician immediately.

General guidance and management include patient awareness and early intervention. Stomatitis/oral mucositis/mouth ulcers due to everolimus should be treated using local supportive care. Evaluation for herpes virus or fungal infection should be considered. Patients should be informed about the possibility of developing mouth ulcers/ oral mucositis and instructed to report promptly any signs or symptoms to their physician. Patients should be educated about good oral hygiene, instructed to avoid spicy/acidic/salty foods, and should follow the following guidelines:

- For mild toxicity (grade 1), use conservative measures such as non-alcoholic mouth wash or salt water (0.9%) mouth wash several times a day until resolution.
- For more severe toxicity (grade 2 in which case patients have pain but are able to maintain adequate oral alimentation, or grade 3 in which case patients cannot maintain adequate oral alimentation), the suggested treatments are topical analgesic mouth treatments (i.e., local anesthetics such as benzocaine, butyl aminobenzoate, tetracaine hydrochloride, menthol, or phenol) with or without topical corticosteroids, such as triamcinolone oral paste 0.1% (Kenalog in Orabase®).
- Agents containing alcohol, hydrogen peroxide, iodine, and thyme derivatives may tend to worsen mouth ulcers. It is preferable to avoid these agents.
- Antifungal agents must be avoided unless a fungal infection is diagnosed. In particular, systemic imidazole antifungal agents (ketoconazole, fluconazole, itraconazole, etc.) should be avoided in all patients due to their strong inhibition of everolimus metabolism, therefore leading to higher everolimus exposures. Therefore, topical antifungal agents are preferred if an infection is diagnosed. Similarly, antiviral agents such as acyclovir should be avoided unless a viral infection is diagnosed.

#### **6.3.2.4 Management of hepatitis reactivation**

Both chemotherapy ([Yeo et al 2004](#)) and mTOR inhibition ([Guo et al 2007](#)) may cause reactivation of hepatitis B.

[Table 6-5](#) provides details of monitoring and prophylactic therapy according to the screening results of viral load and serologic markers testing. If the patient is already known to have a chronic infection with HBV and is taking anti-HBV medication, the site does not have to wait for the screening HBV results from the local laboratory prior to the first dose of the study treatment.

**Table 6-5 Action to be taken based on hepatitis B screening results**

	Result	Result	Result	Result	Result
HBV-DNA	+	+ or -	-	-	-
HBsAg	+ or -	+	-	-	-
HBsAb	+ or -	+ or -	+ and no prior HBV vaccination	+ or -	- or + with prior HBV vaccination
HBcAb	+ or -	+ or -	+ or -	+	-
Recommendation	Prophylaxis treatment should be started 1-2 weeks prior to first dose of study treatment. Monitor HBV-DNA approximately every 4-8 weeks (from Visit 2 and onwards)	No prophylaxis Monitor HBV-DNA approximately every 4 weeks (from Visit 2 and onwards)			No specific action

Antiviral prophylaxis therapy should continue for at least 4 weeks after last dose of study treatment. For hepatitis B reactivation, definition and management guidelines see [Table 6-6](#).

**Table 6-6 Guidelines for management of hepatitis B**

HBV reactivation (with or without clinical signs and symptoms)*	
For patients with baseline results: Positive HBV-DNA OR Positive HBsAg ----- Reactivation is defined as: [Increase of 1 log in HBV-DNA relative to baseline HBV-DNA value OR new appearance of measurable HBV-DNA]	Treat: Start a second antiviral AND Interrupt study treatment administration until resolution: - ≤ baseline HBV-DNA levels  If resolution occurs within 28 days, study treatment should be re-started at one dose lower, if available. (see Table 6-2 Study drug dose reductions) If the patient is already receiving the lowest dose of study drug according to the protocol, the patient should restart at the same dose after resolution. Both antiviral therapies should continue at least 4 weeks after last dose of study drug. If resolution occurs > 28 days, patients should discontinue study treatment but continue both antiviral therapies at least 4 weeks after last dose of study drug.
For patients with baseline results: Negative HBV-DNA and HBsAg AND [Positive HBsAb (with no prior history of vaccination against HBV), OR positive HBcAb] ----- reactivation is defined as: New appearance of measurable HBV-DNA	Treat : Start first antiviral medication AND Interrupt study drug administration until resolution: ≤ undetectable (negative) HBV-DNA levels If resolution occurs within 28 days, study drug should be re-started at one dose lower, if available. (see Table 6-2 Study drug dose reductions) If the patient is already receiving the lowest dose of study drug according to the protocol, the patient should restart at the same dose after resolution. Antiviral therapy should continue at least 4 weeks after last dose of study drug. If resolution occurs > 28 days, patients should discontinue study drug but continue antiviral therapy at least 4 weeks after last dose of study drug.

\* All reactivations of hepatitis B are to be recorded as grade 3 (CTCAE v4.03), unless considered life threatening by the investigator; in which case they should be recorded as grade 4 (CTCAE v4.03). Date of viral reactivation is the date on which the rise or reappearance of HBV- DNA was recorded.

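### Tables 6-3 and 6-6 give opposite instructions for a hepatitis B reactivation that meets the combined ALT/AST-bilirubin criterion, and nothing says which governs

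*Protocol*

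**What the plan says.** **Table 6-6 (Protocol 6.3.2.4).** The heading of the table begins "HBV reactivation (with or without clinical signs and symptoms", so it is not limited to mild or silent cases. It has two rows.

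- First row: HBV-DNA or HBsAg positive at baseline. The action is "Interrupt study treatment administration until resolution: - ≤ baseline HBV-DNA levels", followed by "If resolution occurs within 28 days, study treatment should be re-started at one dose lower, if available".
- Second row: HBV-DNA and HBsAg negative at baseline, with HBcAb positive, or HBsAb positive without vaccination. The action is "Interrupt study drug administration until resolution: ≤ undetectable (negative) HBV-DNA levels", followed by "If resolution occurs within 28 days, study drug should be re-started at one dose lower, if available".

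The footnote grades every reactivation as 3 "unless considered life threatening by the investigator; in which case they should be recorded as grade 4". No different action is attached to that higher grade.

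**Table 6-3 (Protocol 6.3.1).** For combined elevation of AST or ALT and total bilirubin the instruction is "Permanently discontinue patient from study treatment". For Grade 4 events in the residual row for other non-hematologic toxicities it is "Discontinue everolimus and treat with appropriate medical therapy". The isolated ALT/AST rows set transaminase levels that must be reached before dosing resumes. The table has reference lines for pneumonitis and stomatitis but none for hepatitis B.

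**The concern.** A reactivation of hepatitis B is itself a cause of raised transaminases and bilirubin, so one patient can fall under both tables on the same day. If HBV-DNA then clears inside 28 days, Table 6-6 directs a restart, while the combined row of Table 6-3 directs a permanent stop. Two investigators who each follow the protocol could act in opposite ways after the same icteric hepatitis. One of those actions re-exposes the patient to a drug that Section 6.3.2.1 describes as immunosuppressive and associated with hepatitis B reactivation.

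The safety tables are touched as well. SAP 2.8.1.4 tabulates adverse events leading to discontinuation of study drug separately from those requiring dose adjustment or interruption, and SAP 2.4.5 counts reductions. The same event could be counted differently from site to site.

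**Working it through.** No sample size, power or event count is involved, so the check sets the texts side by side.

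**1. Who can reach Table 6-6.** Exclusion criterion 14 rules out quantifiable HBV-DNA and/or positive HBsAg, which appears to empty the first row, although Section 4.1, Section 6.3.2.1 and Table 6-5 still plan for such patients. Patients in the second row are not excluded. Table 6-5 gives them no prophylaxis and HBV-DNA monitoring about every 4 weeks. The point therefore rests on the second row.

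**2. Combined criterion.** Take a second-row patient with normal baseline liver tests who reactivates, has ALT above 3 x ULN with bilirubin above 2 x ULN and no cholestasis, and whose HBV-DNA is undetectable by day 28.

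| Source | Test applied | Instruction |
|---|---|---|
| Table 6-6, second row | HBV-DNA only | Restart study drug one level lower, if available |
| Table 6-3, combined row | ALT/AST and bilirubin | Permanent stop of study treatment |

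The instructions are opposite. The combined row has no carve-out for a viral cause.

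**3. Grade 4.** Take a reactivation recorded as Grade 4 that clears HBV-DNA by day 28. Table 6-6 still restarts. Table 6-3 does not name hepatitis B reactivation, so the event reaches it only through the residual non-hematologic row, which discontinues everolimus. The overlap exists but depends on reading that residual row as applying.

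**4. Recovery conditions.** For isolated ALT/AST above 10 and up to 20 x ULN, Table 6-3 holds the dose until values return to baseline or below, then lowers it one level. Table 6-6 also holds and then lowers one level, but waits for HBV-DNA. These conditions can be applied together. The gap is that no text says whether both must be met.

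**5. Does anything set precedence?**

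- Section 6.3.2 is headed as additional to 6.3.1, not as replacing it.
- The text under Table 6-5 sends the reader to Table 6-6 for managing reactivation, but does not say that it overrides Table 6-3.
- The general rule that the worst toxicity so far drives dose changes does not mention Table 6-6.
- The conservative-action footnote to Table 6-3 applies only when the combined thresholds are not met.
- The combined row sends the reader to 6.3.2.1, which is now the infection section and asks the investigator only to consider interrupting or discontinuing.
- Section 7.1.4 requires a stop for adverse events or laboratory abnormalities as outlined in Section 6. That leads back to the same two tables.

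**6. Scale.** The documents give no rate. Purely as an assumption, let 20% to 50% of about 80 everolimus patients be in the monitored antibody-positive group and 1% to 5% of these reactivate. Low end: 80 x 0.20 x 0.01 = 0.16. High end: 80 x 0.50 x 0.05 = 2.0. These figures count all reactivations. A conflict needs one that also meets the combined criterion or is Grade 4, and that clears HBV-DNA within 28 days, so the affected number is a subset of 0.16 to 2.

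**The case against.** The strongest defence is that Table 6-6 is the specific rule for hepatitis B and a specific rule normally displaces a general one. Against the residual Grade 4 row this has force: a reader might infer that Table 6-3 plainly requires a permanent stop for any life-threatening reactivation, but the documents do not support that. Hepatitis B is not named there, the cell stops everolimus without calling the stop permanent, and Section 6.1.4 lets the other study treatment continue. Against the combined ALT/AST-bilirubin row the defence fails, because that row is equally specific to the liver picture and contains no viral exception.

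A reader might also treat the isolated-transaminase rows as a third opposite instruction. They are not: hold and then reduce appears in both tables, and only the recovery test differs.

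It can further be said that Table 6-3 is labelled as recommended, that Section 6.3.1 says its guidelines may be applied, and that Section 7.1.4 tells the investigator to stop when continuing would be detrimental. This stands to the extent that one cannot say sites would diverge, only that they could. None of these texts says which table governs.

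Finally, the default grade is 3, and for Grade 3 the residual row also interrupts and allows consideration of a lower dose. Most reactivations would therefore raise no conflict with that row.

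**Conclusion.** The inconsistency is real and explicit for one situation: a reactivation that meets the combined ALT/AST-bilirubin criterion and whose HBV-DNA recovers within 28 days. It is a weaker, interpretive gap for reactivations recorded as Grade 4, and an unanswered question about cumulative conditions for isolated transaminase elevation.

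The number affected is probably less than one or two patients, on assumed inputs that the documents neither give nor contradict. It would be wrong to infer that every expected reactivation brings a stop-versus-restart conflict. Even the assumed upper bound of 2 reactivations is 2/160 = 1.25% of the planned sample, so the effect on discontinuation and dose-reduction counts is negligible. The point rests on patient safety: contradictory written instructions after a severe hepatic event. It should be corrected. This review takes no position on which instruction is clinically right.

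**What to change.** Reconcile Tables 6-3 and 6-6:

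1. State which table governs when a reactivation meets the combined ALT/AST-bilirubin criterion, and which governs when it is recorded as Grade 4.
2. State whether the ALT/AST recovery conditions in Table 6-3 must be met in addition to HBV-DNA recovery before any restart.
3. Add a hepatitis B reference line to Table 6-3, as already exists for pneumonitis and stomatitis.

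The content of each answer is a clinical decision for the sponsor. The cost is about one sentence in Table 6-6 and one cross-reference line in Table 6-3, made by amendment or by letter to sites. It adds no patients, visits or procedures and leaves the statistical analysis unchanged.
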